**iii. Benefits**

The subject will receive no benefit other than financial compensation for participating in this study. In general, this study will provide a benefit to future e-cig users as the findings will be reported to the FDA and inform policy, both for reducing toxicity (if any) and to identify harmful effects for consideration as a potential cessation device. The risk for the subject is no greater than a patient of bronchoscopy in a clinical setting. The OSU Wexner Medical Center's standards of care for this procedure are followed. Research results will not be returned to the subject.

**iv. Reporting of adverse events**

See attached DSMP.

**v. Premature Removal of Participant**

See attached DSMP.

**vi. Study Termination Procedures**

The Ohio State University has the right to suspend or permanently close the research study at any time.

**vii. Completion of study**

A participant is considered to have completed the research study when he or she completes all data collection and specimen donation, and their follow-up bronchoscopy. They will be called at three months after the second bronchoscopy procedure to assess their recent tobacco use history and health status.

## g. Statistical Methods

### i. Data Analysis Plan

The analytical plan does not change due to the increase in intervention period from 4 to 8 weeks.

Descriptive statistics and clustering (e.g., principal components analysis [PCA]), will be performed for all biomarker data measured at the different visits. Baseline data (1st bronchoscopy) will then be compared between the four groups (3 conditions and control) using a one-way analysis of variance (ANOVA). The non-parametric Kruskal-Wallis test (continuous or ordinal variables) or the chi-square test (categorical variables) will be applied when the normality assumption of the data is not met. We will compare controls to complete substitution with the SREC (with and without nicotine) or NRT conditions. Generalized linear models (GLM) will be employed with measurement (cell count, gene expression, etc.) as the dependent variable, a covariable for baseline measure, and a main effect of arm. Other relevant variables that are associated with the biomarker results, e.g., baseline smoking, FTND, or gender will also be included in our models as they are potential confounders. We also will assess batch effects and include batch as a co-variable in the model (all samples will be analyzed at the same time, except for cell counts). We plan to use baseline molecular measurement as a covariable rather than modeling the change between baseline and follow-up because the former is more powerful [300]. Given the large dynamic range of the cell count and the 'omics data, we will initially consider a normal distribution. If the data are determined to deviate from normality, we will log-transform the data or assume a non-normal distribution of residuals (such as Poisson) for the GLM. Urine PG will be measured at the 2nd bronchoscopy visit and compared to baseline to verify e-cig use. As an exploratory analysis, urinary PG will be used as the exposure predictor variable assessing the biomarker results as dependent variables. Urine anatabine, urine anabasine and nicotelline will be used to confirm complete substitution or a predictor variable for smoking reduction. The cotinine level will be used as a surrogate for smoking reduction.

The 'omics' (miRNA, mRNA, proteomics and metabolomics) analysis and visualization of the data will be performed in the R statistical language. Data will be log2-transformed and normalized using either quantile normalization for gene expression (miRNA and mRNA) or TIC/MSTUS normalization for metabolomics [301]. Unsupervised clustering analysis, including PCA and hierarchical clustering will be performed to visualize natural clusters in the dataset and evaluate data quality. Multiple testing corrections using the Benjamini and Hochberg False Discovery Rate (FDR) will be performed [302]. Significantly altered genes and metabolites will be defined as those with FDR corrected p-value < 0.05 and fold changes > 2 or > 1.5, respectively. Identified genes or metabolites will be used to identify relevant networks and pathways using Ingenuity Pathways Analysis. For gene expression, we will further study associations between miRNA-mRNA pairs based on publically available target prediction databases such as TargetScanHuman, miRDB, miRWalk2.0 and others [303-308]. Global integrative analysis, through correlations, will be performed using Partek software.

Understanding the epigenomic/genomic/proteomic/environment context and regulation of metabolic phenotypes will expand our knowledge of the effects of e-cig on lung biology, and could contribute to finding successful interventions, including accurate predictions of e-cig related adverse effects. Typical omics integration methods include logistic regression or correlations among omics measurements (when measured in the same samples), intersection of gene/protein/metabolite lists (when measured in different samples), or further downstream integration by assessing alterations in pathways [309-311]. Because our omics measurements will be made in the same sample, we will be able to directly assess relationships between our molecular data through regression or correlation analyses. Of note, typical regression/correlation approaches are not appropriate for low sample numbers, and they do not readily adjust for differences in sample size between phenotype groups or for potential confounders. Another approach, which we propose here, is to directly test whether associations between miRNA or gene or cytokine and metabolite levels are specific to a group assignment. To test this, we will apply a novel linear model approach recently developed by [name] for these types of analysis:  $m = g + t + g:t$ , where  $m$  are metabolite abundances,  $g$  are miRNA or gene or cytokine levels,  $t$  is treatment group (e.g. SREC vs. continued smoking), and  $g:t$  is the interaction between miRNA or gene or cytokine level and treatment group. A statistically significant  $g:t$  interaction p-value would indicate that gene (or miRNA or cytokine):metabolite relationships are present in one treatment group and not the other. Pathway enrichment analysis of associated miRNA, genes,

cytokines, and metabolites (resulting from the linear models) will be performed in Ingenuity Pathway Analysis to pinpoint altered pathways and better understand how the epigenomic/genomic/proteomic/environment affects metabolic phenotypes associated with e-cig usage. Furthermore, miRNA, genes, cytokines, and metabolites involved in treatment-specific associations will be used to predict treatment group, in an effort to produce an e-cig inflammation signature. Ten-fold cross-validations of various linear-based and non-linear based machine learning methods will be tried (e.g. Random forests, naïve Bayes, Lasso) and the resulting specificity and sensitivity will be assessed to select the best performing model. Of note, the cross-validation will help ensure that the predictive models are not overfit and could be predictive on new validation data. The contribution of input molecular measurements (gene, cytokines, miRNAs, metabolites) to the model will be assessed to define the minimal set of features that yield the optimal cross-validated models.

All statistical analysis and visualization of differential methylation will be performed using Partek Genomics Suite (Partek). Raw intensity data (idat files) will be imported into Partek and normalized using the Subset-quantile Within Array Normalization (SWAN). Any probes with detection  $P > 0.05$  and probes in Y- chromosome to avoid sex-specific methylation bias will be filtered out before further analysis. To identify differentially methylated CpGs, methylation  $\beta$ -values will be converted to M-values by logit-transformation for the statistical modeling purpose. For preliminary identification of patterns in DNA methylation, unsupervised hierarchical clustering among the groups of samples will be performed. The Euclidian distance among the groups of samples will be calculated by the average linkage. In order to assess variance among samples, Principal Component Analysis (PCA) will be done. To characterize the methylation patterns, differentially methylated CpGs will be classified by enhancer, CpG island or its neighbors [2 kb regions upstream and downstream of the CpG islands (shores) or 2 kb regions upstream and downstream of the CpG island shores (shelves)] and functional promoters [within 1500 bp of a transcription start site (TSS) (TSS1500), within 200 bp of a TSS (TSS200), 5' untranslated regions (5'UTR), first exon (1stExon)], and other regions (body, 3'UTR, or intergenic). Separately, we will also analyze for DNA methylation levels of miRNAs promoter regions to investigate if miRNAs methylation appears to be altered between the groups. When we have a full sample, multiple testing corrections will be performed using the Benjamini and Hochberg False Discovery Rate (FDR with significantly differential methylation levels defined at corrected  $P < 0.05$ ). Genes corresponding to differentially methylated CpGs will be used for identification of gene networks and biological pathways using the Ingenuity Pathways Analysis. In addition, we will examine differences in methylation for candidate genes that have been previously shown to be associated with lung cancer and/or with smoking using the same methods. To understand the potential biological contribution of differentially methylated CpGs to coding gene or miRNA expression (from on-going pilot study), we will correlate between the differentially methylated CpGs (M-value) from the EPIC methylation array and matched coding gene or miRNA expression (log2 transformed intensity) from the Affymetrix Human Transcriptome array or Affymetrix GeneChip miRNA array using Spearman correlations. To determine if differences in DNA methylation are associated with cytokines levels (as measured for IL-6, IL- 10, TNF-alpha, and TNF-alpha in BAL in the current on-going study), we will select CpGs corresponding to IL-6, IL- 10, and TNF-alpha from the EPIC methylation array (targeted analysis) and correlate between methylation levels and corresponded cytokines. Correlations controlling for possible confounders (e.g., age) will be explored using multiple linear regression models. We will also explore if the correlation between methylation and cytokine levels may be mediated by gene expression of cytokines using interaction analysis.

Study staff and biostatisticians will monitor the success of RDS and incorporate appropriate analyses to address bias if appropriate.

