mRNA expression: The differences in mRNA expression have been well described for smokers versus non-smokers, and used for the early detection of lung cancer including gene expression related to inflammation [41, 42, 50, 81-85]. Expression profiles for genes that are up- and down-regulated have been described and shown to cluster with smoking status [81]. In 16 smokers compared to non-smokers, genes were differentially expressed relevant to the pathogenesis of COPD, including those coding for inflammatory cytokines and innate immunity, response to oxidants and xenobiotics, and general cellular processes [82]. Dose-response mRNA expression changes to urine cotinine have been identified in 121 subjects who were smoking the equivalent of only a few cigarettes per day [42]. In this large cross-sectional study, pathway analysis implicated genes involved in the metabolism of xenobiotics, arachidonic acid metabolism, and oxidative stress responses.

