Understanding the epigenomic/genomic/proteomic/environment context and regulation of metabolic phenotypes will expand our knowledge of the effects of e-cig on lung biology, and could contribute to finding successful interventions, including accurate predictions of e-cig related adverse effects. Typical omics integration methods include logistic regression or correlations among omics measurements (when measured in the same samples), intersection of gene/protein/metabolite lists (when measured in different samples), or further downstream integration by assessing alterations in pathways. Because our omics measurements will be made in the same sample, we will be able to directly assess relationships between our molecular data through regression or correlation analyses. Of note, typical regression/correlation approaches are not appropriate for low sample numbers, and they do not readily adjust for differences in sample size between phenotype groups or for potential confounders. Another approach, which we propose here, is to directly test whether associations between miRNA or gene or cytokine and metabolite levels are specific to a group assignment. To test this, we will apply a novel linear model approach recently developed by [name] for these types of analysis: $m = g + t + g:t$, where m are metabolite abundances, g are miRNA or gene or cytokine levels, t is treatment group (e.g., SREC vs. continued smoking), and g:t is the interaction between miRNA or gene or cytokine level and treatment group. A statistically significant g:t interaction p-value would indicate that gene (or miRNA or cytokine):metabolite relationships are present in one treatment group and not the

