- 4) For mtDNA features, Model 1 is also used. CN is expected to be Gaussian, while mutation rate is expected to be low counts; therefore, a t-test was powered for CN and Poisson [3] for mutation rate. Because there will only be several comparisons here, the significance threshold used for power corresponds to one expected false discovery per 100 tests. We believe that this threshold is a good balance between potential Type I and Type II errors, given the number of tests. The coefficient of variation was calculated from results in the

literature, as cited in the main body of the protocol. For CN, with 21 samples per group, considering a significance threshold of 0.01, a two-sided, two-sample t-test achieves 80% power to detect an 1.4 fold difference between arms considering a coefficient of variation of 0.32 [4]. For mutation, Poisson regression achieves 80% power to detect a mutation rate ratio of 2.7 between arms considering a significance threshold of 0.01 and 21 samples per group [5].

- 5) For associations between mtDNA and other 'omics features, we assume the regression model [6]:

$$\text{Followup_Expression} = \text{Baseline_expression} + \text{arm} + \Delta\text{mtDNA feature} + e,$$

Where $\Delta\text{mtDNA} = \text{Followup_mtDNA} - \text{Baseline_mtDNA}$. We consider this model across all arms. The effect of arm is included as a covariable to ensure that associations are not simply due to both features being associated with arm; rather, we are looking for a more direct relationship. Again, we consider a significance threshold corresponding to one expected false discovery per 10,000 tests, as described above. To generalize, we assume unit standard deviations of the dependent and independent variables (each feature will have a different standard deviation, so results are calculated in terms of standard deviations). With 84 samples, considering a significance threshold of $p=0.0001$ and unit standard deviations for dependent variable residuals and ΔmtDNA features, linear regression achieves 80% power to detect a slope of 0.48.

- 6) For comparing mtDNA features between nasal and bronchial samples, mixed Poisson or mixed Gaussian will be employed with a random effect for subject, and a main effect for location (bronch vs. nasal):

$$\text{Feature} = \text{sample\&rand} + \text{location} + e.$$

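### In contrasts with continued smoking, the gene-metabolite interaction model has no term for current smoke exposure, so two unlinked features that both follow smoke dose can appear as a treatment-specific association

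*Protocol*

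**What the plan says.** Protocol 4.g.i and SAP item 2 give the integration model as m = g + t + g:t, "where m are metabolite abundances, g are miRNA or gene or cytokine levels, t is treatment group". The example offered for t is SREC against continued smoking. A significant interaction is read as showing that the "relationships are present in one treatment group and not the other". The features found this way go to pathway enrichment, which is meant to explain metabolic phenotypes linked to e-cig use. They also go to a classifier of treatment group intended to yield an e-cig inflammation signature.

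Just before the model, the plan says of typical regression and correlation that "they do not readily adjust for differences in sample size between phenotype groups or for potential confounders".

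Covariates are mentioned earlier in the same section, for the arm-comparison models: "Other relevant variables that are associated with the biomarker results, e.g., baseline smoking, FTND, or gender will also be included in our models". Smoke-specific markers are planned, and their stated use is: "Urine anatabine, urine anabasine and nicotelline will be used to confirm complete substitution or a predictor variable for smoking reduction". None of them is expressly assigned to the g:t model. The only planned analysis of smoking dose against biomarkers is exploratory and uses baseline samples. No power, error rate or significance threshold is given for g:t, and the text does not say which visit's levels enter it.

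**The concern.** Arm is randomised; the gene level g is not. Controls keep smoking their usual brand, and entry requires at least five cigarettes a day with no stated upper limit, so their dose differs from person to person. After complete switching, dose is near its floor for everyone. The protocol's background says that expression follows dose ("Dose-response mRNA expression changes to urine cotinine have been identified in 121 subjects") and that metabolomics can show changes caused by smoke constituents. Dose alone can therefore make a gene and a metabolite correlate among controls and not among switchers. The g:t test would flag the pair although neither feature acts on the other.

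At stake is the reading of these pairs. The plan would carry them forward as evidence on how gene regulation affects metabolism under e-cig use, when some may reflect only a difference in the spread of smoke exposure. Among contrasts with continued smoking, the effect is strongest where switching is most complete.

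**Working it through.** **Sample size.** Protocol 4.g.ii enrols 32 per arm with 66% retention: 32 × 0.66 = 21.12, so 21 per arm, and 4 × 21 = 84. This reproduces the plan's figure. There is no stated g:t error rate to reproduce.

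**Model for the check (assumed).** Let z be log smoke dose, with SD 1 among controls. Set g = a·z + e1 and m = a·z + e2, with independent errors of SD 1 and no direct link. Among smokers each feature then has R² = a²/(1 + a²) on dose. The documents give no R², so a range is used.

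**Expected interaction.** The slope of m on g is a²/(1 + a²) = R² in controls. In switchers with dose variance s² it is a²s²/(1 + a²s²). The g:t coefficient is the second minus the first.
- Full abstinence (s² = 0): g:t = −R², for example −0.50 at R² = 0.5.
- Switchers' dose SD half that of controls, R² = 0.49 (a² = 0.961): 0.240/1.240 − 0.49 = −0.30.
- Equal spread: 0.

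This bias does not depend on sample size.

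**Rejection of g:t by simulation, 21 v 21, full abstinence, unlinked features.**

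| R² on dose (assumed) | As written, 0.05 | As written, 0.0001 | Baseline smoking added, 0.05 | BR2 dose marker added (error SD 0.3), 0.05 |
|---|---|---|---|---|
| 0.1 | about 6% | – | – | – |
| 0.3 | 15% | 0.1% | 10% | about 5% |
| 0.5 | 34% | 0.7% | 23% | about 7% |

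The 0.0001 level is the one the plan uses for omics power. Nominal there is 0.01%, so 0.1% and 0.7% are about 10 and 70 times nominal. With 200 per arm and R² = 0.25 (correlation 0.5 with dose), rejection at 0.05 reaches 70%.

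**Baseline smoking.** The fourth column assumes a correlation of 0.8 between baseline and follow-up dose. Even if the two were identical in controls, 16% would remain at R² = 0.49. A single baseline slope is shared by both arms, while dose acts only in the smoking arm. The protocol also says that controls may cut down during the study.

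**Incomplete switching.** At R² = 0.49, with switchers' dose SD at 0.25, 0.5, 0.75 and 1.0 times that of controls, rejection at 0.05 is 26%, 15%, 7% and 5%. If instead 30% of switchers still smoke (mean −1, SD 1) and the rest sit at a floor d units below that mean, their dose variance is 0.3 × 0.7 × d² + 0.3. For floors of −1, −3 and −6 (d = 0, 2, 5) this is 0.30, 1.14 and 5.55. At R² = 0.5 the rejection rates are about 15%, 5–6% and 28–29%. In the last case switchers vary more than controls and the sign reverses: 5.55/6.55 − 0.50 = +0.35. No single relapse figure can be quoted without stating the floor.

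**Marker error.** At R² = 0.5, raising the error SD of the BR2 marker to 0.5 or 0.75 leaves about 12% or 18–19%.

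**The case against.** The strongest reply is that the test answers its own question. The plan asks whether an association is specific to a group. If smoke dose creates the association in smokers and switching abolishes it, then it is group-specific, and randomised switching caused the difference. Smoke-driven features are also legitimate predictors of arm. This stands. A reader might infer that every such rejection is a false positive, and the documents do not support that. The problem arises when g:t is read as a link between gene and metabolite, as the pathway text does.

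A second reply is that the formula is schematic. SAP Model 1 is also written without covariates, although SAP item 2 says they will be added, and its list of examples is open. So the bare formula does not prove that covariates are barred. The fair statement is that no follow-up smoke term is assigned to this model, and that the smoking covariate actually named is the baseline one.

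Third, SAP item 5 might be taken as a precedent, since there "The effect of arm is included as a covariable to ensure that associations are not simply due to both features being associated with arm". It is not one for a dose term: item 5 adjusts for arm, the g:t model already contains t, and item 5 has no dose term either.

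Fourth, follow-up exposure is post-randomisation and is a main route by which switching acts, so adjusting for it changes the question. It also costs power. For a true link present only in smokers (assumed coefficient 0.75, R² 0.5), power at 0.05 falls from 72% to 62%. This stands, and it argues against making survival of the adjusted test a compulsory condition.

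**Conclusion.** The point holds for contrasts with continued smoking that use follow-up levels. There the planned interaction can reflect unequal spread of smoke exposure instead of a gene-metabolite link, and baseline smoking does not remove this. The size is conditional on the assumed R²: negligible near 0.1, material from about 0.3 upwards with full abstinence, and smaller as switchers' exposure varies more like that of controls. A stricter threshold lowers the absolute rate but not the bias.

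A reader might infer that the trial's treatment comparisons are compromised. They are not affected in this way: Model 1 compares randomised arms and does not rest on g. Nor are contrasts among the nicotine SREC, placebo SREC and NRT arms, provided switching is complete. This is a recommended improvement to a downstream analysis, not a fault in the primary comparison.

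**What to change.** In Protocol 4.g.i and SAP item 2, state that g and m are follow-up levels. For contrasts with continued smoking, also fit m = g + t + g:t + log BR2 smoke marker. Use urine nicotelline or anatabine/anabasine, which are already planned at both bronchoscopy visits. Do not use cotinine: the protocol's laboratory section describes it as a nicotine metabolite, so it cannot isolate smoke dose in the nicotine SREC or NRT arms. Report g:t with and without the term. Where g:t is lost after adjustment, describe the pair as compatible with differing smoke exposure, not as an e-cig-specific link, in the pathway and signature claims.

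The cost is one degree of freedom, a sentence or two in each document, and no new data. The adjusted model loses some power for true links, leaves residual artefact from marker error, and is conditional on post-randomisation exposure. It should therefore sit beside the planned estimate and not act as a mandatory gate.
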